#### c) **Inclusion/exclusion criteria**

Inclusion : Patients aged 18 and above, able to give informed consent

COVID-19 test positive or presumptive positive awaiting COVID testin or results by following criteria: fever, cough and shortness of breath

Overall Study Exclusion Criteria :

Unable to give informed consent  
Prisoner/ institutionalized patient  
Under age 18

Exclusion from Fluoxetine Arm:

Active bleeding requiring blood products  
Bipolar disorder not on mood stabilizing medication\*  
Known allergy or hypersensitivity to fluoxetine  
Currently taking the following medications : MAO I, pimozide, thioridine  
Currently taking hydroxychloroquine  
Pregnant or breastfeeding (pregnancy questionnaire attached)  
For hospitalized patients : QTc greater than 500 ms  
\*Hospitalized patient may be on hydroxychloroquine if QTc<500 and the primary attending approves

Exclusion from Blood Sample Provision:

Pregnant  
Self-report of under 110 pounds

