#### b) **Method of treatment assignment**

Single arm patient centered clinical trial

At study entry, participants will consent study participation via daily monitoring and will choose whether to participate in the activity monitoring, cytokine assessment and drug treatment portions of the trial. Participants who do not choose to take fluoxetine will serve as the control subjects. Additionally, patients will have the choice weekly to decide to start, continue, or discontinue the fluoxetine. See figure below :

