#### **Aim 1 : Hospitalization rates**

Assumptions:

1. 2/3 of patients who enter the trial will choose to take fluoxetine
2. 10% of COVID-19 + patients will progress to a clinical condition requiring hospitalization
3. Fluoxetine treatment decreases hospitalization rate by 50%

Sample Size : 312 in the no medication group and 624 in the 2 fluoxetine groups, for a total sample size of 936. This sample size is very achievable given the current coronavirus pandemic.

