**Prevention of Hospitalization**

Hospitalization, no medication	10%
Hospitalization, Fluoxetine	5%
Alpha	0.05
Beta	0.2
Power	0.8
Sample Size	
No medication	312
Fluoxetine, low or high	624
Total	936

Aim 2 : Intubation in those hospitalized

Assumptions

1. 10% of patients requiring hospitalization for COVID-19 + will progress to intubation
2. Fluoxetine treatment decreases intubation rate by 20%

Aim 2: Death in those hospitalized

Assumptions

1. 1% of patients requiring hospitalization for COVID-19 + will die during that hospitalization
2. Fluoxetine treatment decreases mortality rate by 20%

**Sample Size** : 3213 in the no medication group and 3213 in the fluoxetine groups, for a total sample size of 6426. These sample sizes will not be achievable in this pilot study. Data from Aims 3 and 4 will therefore be used qualitatively for the gathering of pilot data.

Prevention of intubation, death	
Sample Size	
No medication	3213
Fluoxetine	3213
Total	6426
Prevention of Intubation	

Intubation, death in no medication	10%
Intubation, death in fluoxetine	8%
Alpha	0.05
Beta	0.2
Power	0.8

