#### **4) Planned data analysis**

Aim 1, 2, 3 : Descriptive statistics,

Compare rates of primary and secondary outcome measures in subjects receiving fluoxetine with those not receiving fluoxetine by Student t-test and Chi-square test as appropriate.

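### Patients barred from fluoxetine stay in the study and, as the analysis is worded, count as untreated comparators, so the Aim 1 comparison may be partly confounded by contraindication

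*Combined protocol and SAP*

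**What the plan says.** Section 3c has two separate lists. The overall study exclusions are only inability to consent, prisoner or institutionalized status, and age under 18. A second list, headed "Exclusion from Fluoxetine Arm", covers active bleeding that needs blood products, bipolar disorder without a mood stabilizer, fluoxetine allergy, the named interacting drugs, hydroxychloroquine, and pregnancy or breastfeeding. One further item is limited to inpatients: "For hospitalized patients : QTc greater than 500 ms". A footnote relaxes one bar: "Hospitalized patient may be on hydroxychloroquine if QTc<500 and the primary attending approves".

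On who is a control, section 3b says: "Participants who do not choose to take fluoxetine will serve as the control subjects". It adds that "patients will have the choice weekly to decide to start, continue, or discontinue the fluoxetine. See figure below"; that figure is not in the available text. Section 4 compares primary and secondary outcomes "in subjects receiving fluoxetine with those not receiving fluoxetine by Student t-test and Chi-square test as appropriate". Section 3g lists medications, medical history and comorbidities as variables, but section 4 gives them no role in the analysis.

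The Aim 1 sample size in section 3d is "312 in the no medication group and 624 in the 2 fluoxetine groups", with two thirds of entrants assumed to choose the drug. It makes no allowance for patients who cannot choose it.

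**The concern.** Withholding fluoxetine for safety while still observing these patients is sensible. Using them as the untreated comparison is what causes difficulty. A barred patient can enter only one of the two groups while the bar applies, so whatever the bar says about prognosis loads entirely onto the control side. A difference in hospitalization can then appear with no drug effect, or a real effect can be masked.

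This differs from ordinary self-selection. Eligible patients who decline may resemble some who accept, so measured covariates can help. For patients under a bar with no treated counterparts, covariate adjustment has to extrapolate.

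The comparison most exposed is Aim 1, the one the trial is sized for. The bars that matter there are active bleeding, unstabilized bipolar disorder, allergy, the interacting drugs, hydroxychloroquine, and pregnancy or breastfeeding. The QTc bar applies only to inpatients, so it bears on intubation and death, not on hospitalization.

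**Working it through.** **Inputs from section 3d.** Hospitalization 10% without medication and 5% with fluoxetine; alpha 0.05; power 0.80; 312 controls and 624 takers. Sidedness is not stated; two-sided reproduces the figures.

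**Reproducing the plan's figure.** Pooled normal approximation for two proportions, ratio r = 2, pooled rate p̄ = (0.10 + 2 × 0.05)/3 = 0.0667:

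n = [1.96 √(p̄(1 − p̄)(1 + 1/2)) + 0.8416 √(0.10 × 0.90 + 0.05 × 0.95/2)]² / 0.05² = (0.5988 + 0.2839)² / 0.0025 = 311.6, so 312 controls, 624 takers and 936 in all. This matches exactly. The point therefore concerns comparability, not a wrong sample size.

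**Bias illustration.** The documents give neither f, the share of controls barred at entry, nor k, their risk relative to eligible patients. Both are assumed. With no drug effect and 10% risk in eligible patients:

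- Control rate: p_c = 0.10(1 − f) + 0.10 k f
- Expected risk ratio: 0.10/p_c
- Chance of a false significant benefit: Φ[(p_c − 0.10 − 1.96 SE₀)/SE₁], where SE₀ is the pooled and SE₁ the unpooled standard error with 312 and 624 patients. For false harm, the sign of the difference is reversed.

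Example, f = 10% and k = 2: p_c = 0.110, SE₀ = 0.02111, SE₁ = 0.02140; (0.010 − 0.04137)/0.02140 = −1.466, which gives 7.1%.

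| Barred share of controls | Risk ratio, k = 2 | False benefit, k = 2 | Risk ratio, k = 0.5 | False harm, k = 0.5 |
|---|---|---|---|---|
| 1% | 0.99 | 2.8% | 1.01 | 2.6% |
| 2% | 0.98 | 3.2% | 1.01 | 2.8% |
| 5% | 0.95 | 4.4% | 1.03 | 3.2% |
| 10% | 0.91 | 7.1% | 1.05 | 4.2% |
| 20% | 0.83 | 15.9% | 1.11 | 6.7% |

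The nominal value in each direction is 2.5%. At k = 1 the ratio is 1.00 and the error is 2.5% throughout. At k = 1.5 and f = 5%, false benefit is 3.3%. At k = 0.5 and f = 20%, power against a true 10% versus 5% effect falls from 80.0% to 64.6%.

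**Why a small overall share can matter.** Barred patients all fall on one side. Thirty-one of them are 31/936 = 3.3% of the trial but 31/312 = 10% of controls.

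**Power after restriction.** Same approximation, 10% versus 5%, 624 takers held fixed:

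| Controls leaving | Controls left | Power |
|---|---|---|
| 0% | 312 | 80.0% |
| 5% | 296 | 78.9% |
| 10% | 281 | 77.7% |
| 20% | 250 | 74.9% |

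**The case against.** **Control membership is partly inferred.** Section 3b is the only text that defines controls, and its wording presupposes a choice that barred patients do not have; the missing figure may route them elsewhere. A reader might infer that the plan deliberately designates barred patients as controls. The documents do not go that far. What stands is narrower: section 4 classifies by receipt, and no available text takes these patients out.

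**The size is not shown.** This is correct. A reader might infer a bias in favour of fluoxetine. Nothing in the documents supports a direction, since some bars could mark higher risk and others lower, and some may not be prognostic at all. The distortion is small unless roughly 10% or more of controls are barred and their risk is clearly different.

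**Self-selection is the larger problem.** This is also correct. By the same formula, eligible decliners at an assumed 1.2 times the takers' risk (12% versus 10%) already give 15.9% false benefit, equal to the most extreme doubled-risk row above. Restriction leaves that untouched.

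**Not every barred patient lacks a treated counterpart.** Inpatients on hydroxychloroquine may take fluoxetine if QTc is below 500 and the attending agrees. The claim that treatment is impossible therefore fails for them and holds for the others only while the bar applies.

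**Eligibility may not be known for decliners.** The contraindication review sits in an interview that also covers prescribing, and decliners might not have it. The schedule does not limit that interview to takers, and the baseline intake and medication data are listed for study participants generally, so most of the information should exist. The pregnancy questionnaire would need to be given to everyone.

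**Conclusion.** The concern holds as a gap in the analysis plan with a possible bias in Aim 1, not as a demonstrated bias. It rests on section 4's wording being followed as written and on at least one bar being prognostic for hospitalization. Under the assumed doubled risk, false benefit is 4.4% to 15.9% for barred shares of 5% to 20%; under halved risk the distortion reverses; under equal risk it vanishes. No figure is offered for intubation or death: the documents do not support one, and section 3d says of those sample sizes "These sample sizes will not be achievable in this pilot study". The priority is low to moderate. It is worth correcting because the correction is cheap, and it should be read alongside the larger self-selection problem.

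**What to change.** 1. State in section 4 whether patients barred from fluoxetine count as controls.
2. Record fluoxetine eligibility at study entry for every participant, from the baseline intake, the medication list and the pregnancy questionnaire.
3. Restrict the primary Aim 1 comparison to participants eligible at study entry. Someone barred at entry stays out of it even if they start fluoxetine in a later week. Report all controls as a sensitivity analysis.
4. Restate Aim 1 power for the controls retained.
5. For Aim 2, report barred inpatients separately and descriptively. A QTc rule for controls is not advisable, because QTc is not among the listed variables and may be missing for them. Dropping all inpatients on hydroxychloroquine would discard treated patients whom the protocol permits.

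The cost is a short analysis paragraph and one field per participant, with no new visit if the baseline procedures are carried out for everyone as listed. Power falls by 2.3 points if 10% of controls leave and by 5.1 points if 20% leave, slightly more if any late starters barred at entry also leave the taker group. To keep 312 eligible controls instead, about 312/0.9 = 347 non-takers would be needed at a 10% barred share, or 312/0.8 = 390 at 20%.

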#### **d) Justification of the number of subjects**

All power calculations were done with the clincalc program and assume a dichotomous endpoint in a two independent sample study and are based on achieving the standards of a power of 0.80 and with an alpha of 0.05. Please note, that the assumptions of fluoxetine effect size are based on the absolute most conservative values in the published literature reviewed above.

#### **Aim 1 : Hospitalization rates**

Assumptions:

1. 2/3 of patients who enter the trial will choose to take fluoxetine
2. 10% of COVID-19 + patients will progress to a clinical condition requiring hospitalization
3. Fluoxetine treatment decreases hospitalization rate by 50%

Sample Size : 312 in the no medication group and 624 in the 2 fluoxetine groups, for a total sample size of 936. This sample size is very achievable given the current coronavirus pandemic.

**Prevention of Hospitalization**

Hospitalization, no medication	10%
Hospitalization, Fluoxetine	5%
Alpha	0.05
Beta	0.2
Power	0.8
Sample Size	
No medication	312
Fluoxetine, low or high	624
Total	936

Aim 2 : Intubation in those hospitalized

Assumptions

1. 10% of patients requiring hospitalization for COVID-19 + will progress to intubation
2. Fluoxetine treatment decreases intubation rate by 20%

Aim 2: Death in those hospitalized

Assumptions

1. 1% of patients requiring hospitalization for COVID-19 + will die during that hospitalization
2. Fluoxetine treatment decreases mortality rate by 20%

**Sample Size** : 3213 in the no medication group and 3213 in the fluoxetine groups, for a total sample size of 6426. These sample sizes will not be achievable in this pilot study. Data from Aims 3 and 4 will therefore be used qualitatively for the gathering of pilot data.

Prevention of intubation, death	
Sample Size	
No medication	3213
Fluoxetine	3213
Total	6426
Prevention of Intubation	

Intubation, death in no medication	10%
Intubation, death in fluoxetine	8%
Alpha	0.05
Beta	0.2
Power	0.8

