## **2. Objectives/Specific Aims**

**Aim 1:** Fluoxetine treatment begun early after COVID-19 infection will reduce hospitalizations, intubations, and death from COVID-19 and complications more than no medication

**Aim 2:** Fluoxetine will decrease intubations and mortality in patients hospitalized with COVID-19 infection greater than no medication.

**Aim 3 :** Fluoxetine treatment of COVID-19 infected patients will not cause significant side effects or increase morbidity and mortality compared to no medication

**Aim 4.** Collect blood samples from 40 subjects for future cytokine analysis: both subjects taking fluoxetine and not taking fluoxetine samples taken at baseline and weekly after study initiation.

[figure not shown]

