**f) Primary and secondary outcome measures**

Primary Outcome Measures:

Aim 1 : Rates of Hospitalization

Aim 2 : Rates of Intubation and Death

Aim 3 : Side effect profile

Secondary Outcome Measures:

Aim 1 and 2 : Depression, Anxiety, Suicidal thinking, Days of Illness, Severity of Illness

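### Intubation, death and side effects are tested primary outcomes in two sections and pilot data in another, while the 936 is sized for hospitalization alone

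*Combined protocol and SAP*

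**What the plan says.** **Outcome status.** Section 3f puts three entries under primary outcomes: hospitalization for Aim 1, "Aim 2 : Rates of Intubation and Death" and "Aim 3 : Side effect profile". Section 4 (Planned data analysis) begins with descriptive statistics for Aims 1 to 3. It then compares primary and secondary outcomes between takers and non-takers of fluoxetine by t-test or chi-square, with no order of testing and no division of alpha. Section 2 words Aim 1 more broadly than 3f does: early fluoxetine "will reduce hospitalizations, intubations, and death from COVID-19 and complications more than no medication".

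**Sample size.** Section 3d rests on "achieving the standards of a power of 0.80 and with an alpha of 0.05". For Aim 1 it gives 312 + 624, "for a total sample size of 936. This sample size is very achievable given the current coronavirus pandemic". For Aim 2 it assumes intubation falling from 10% to 8% of hospitalized patients. For death it assumes that "1% of patients requiring hospitalization for COVID-19 + will die during that hospitalization", reduced by 20%. One figure, 3213 per group, is given for both. The text then says: "These sample sizes will not be achievable in this pilot study. Data from Aims 3 and 4 will therefore be used qualitatively".

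**Who is enrolled.** Patients already in hospital can enter. Section 3e lists the hospital as a setting, and the fluoxetine exclusions in 3c include "For hospitalized patients : QTc greater than 500 ms".

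**Interim looks.** The Data Safety Monitoring Board paragraph plans analyses every three months, with early termination for benefit or harm considered under a 2016 guideline. That guideline is not among the 48 references. The Study Timeline puts Review 4 on 4/1/2021, the day overall enrolment ends.

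**The concern.** The sections cannot all be followed. Taken literally, 3d makes side effects, a primary outcome, qualitative and leaves the unachievable Aim 2 as a tested primary outcome. Taken as a numbering slip, it makes intubation and death pilot data, yet 3f and section 4 still call them primary and test them.

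As it stands, a difference in intubation or death could be called a primary finding or pilot data after it has been seen. A null result on those outcomes would be close to uninformative, because the trial has almost no power for them. Separately, because no interim threshold is written out, a reader cannot work out from the plan what error rate lies behind an early claim on hospitalization.

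**Working it through.** **1. The plan's sample sizes.** Inputs from 3d: alpha 0.05, power 0.80; 10% vs 5% at 1:2 (hospitalization); 10% vs 8% at 1:1 (intubation); 1% vs 0.8% at 1:1 (death). Sidedness is not stated; two-sided is inferred because it reproduces the plan's figures. With k the allocation ratio and p̄ = (p0 + k·p1)/(1 + k), the no-medication group size is

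n = [1.960·√(p̄(1−p̄)(1+1/k)) + 0.8416·√(p0(1−p0) + p1(1−p1)/k)]² / (p0−p1)²

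- Hospitalization: p̄ = 0.0667; (1.960 × 0.3055 + 0.8416 × 0.3373)² / 0.0025 = 311.6, so 312 + 624 = 936. This matches, with power 80.0%.
- Intubation: p̄ = 0.09; (1.960 × 0.4047 + 0.8416 × 0.4045)² / 0.0004 = 3212.9, so 3213 per group. This matches.
- Death: p̄ = 0.009; (1.960 × 0.13356 + 0.8416 × 0.13355)² / 0.000004 ≈ 35,001 per group, not 3213.

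A one-sided test (248 controls) or a continuity correction (341 controls) does not give 312. The 936 is therefore one look at one outcome, with no allowance for others.

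**2. What 936 gives for Aim 2.** Hospitalized: 312 × 0.10 = 31.2 and 624 × 0.05 = 31.2. Expected intubations: 31.2 × 0.10 + 31.2 × 0.08 = 5.6. Expected deaths: 31.2 × 0.01 + 31.2 × 0.008 = 0.6. Power is the sum of both rejection tails in the normal approximation, which is rough at such counts:

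| Comparison | 31 + 31 | 312 + 624, all inpatients |
|---|---|---|
| Intubation, 10% vs 8% | 5.9% | 18.5% |
| Death, 1% vs 0.8% | 5.1% | 7.0% |

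The first column is a floor, because it leaves out patients enrolled in hospital. The second is the extreme case.

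**3. Testing three outcomes at 0.05.** Null trials were simulated with hospitalization at 10% in both groups, and intubation 10% and death 1% of hospitalized patients (deaths taken to occur among the intubated), using uncorrected chi-square tests. The chance of at least one false positive is 10.5% when only patients hospitalized from the 936 count. It is about 13.6% with an assumed 300 + 600 further inpatients. The limit for three independent tests is 1 − 0.95³ = 14.3%.

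**4. If some of the 936 are inpatients at entry.** Hospitalization cannot be an outcome for them. Power for 10% vs 5% in the remainder, for assumed inpatient shares:

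| Inpatient share | Remaining | Power |
|---|---|---|
| 10% | 281 + 562 | 76% |
| 20% | 250 + 499 | 71% |
| 30% | 218 + 437 | 66% |

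**5. An example interim threshold.** Assume uniform accrual, with no-medication enrolment over 365 days and fluoxetine over 306 days (closing 2/1/2021, Study Timeline). Information is n0·n1/(n0+n1), divided by its final value 312 × 624/936 = 208. Reviews at days 91, 183, 275 and 365 then hold 26.4%, 53.0%, 79.6% and 100% of the information with no outcome lag. With an assumed 28-day lag they hold 18.2%, 44.9%, 71.5% and 94.8%. With p<0.001 at every look before a final test at 0.05, simulated type I error is 5.1% and power 80% in both cases, and also with a 14-day lag.

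**The case against.** The intent can be read from context. The qualitative-use sentence follows the Aim 2 sizing and is joined to it by a therefore, so intubation and death are evidently meant as pilot data; section 4 also lists descriptive statistics first. This is fair, and it is why the Aims 3 and 4 wording is treated as a probable slip. It does not remove the conflict, because 3f still calls these outcomes primary and section 4 still compares them by test.

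A second objection is that separately stated aims need not form one error family, least of all in a self-described pilot. That stands as a caveat: the 10% to 14% applies only if the three outcomes are treated as one family and each is tested at 0.05.

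A reader might infer more than the documents support in three ways:

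- That Aim 1 can be claimed on any of three outcomes. Section 2 words it broadly, but the 3d heading and 3f both give Aim 1 as hospitalization only. The wording needs aligning; it does not open three routes to a claim.
- That the quarterly looks inflate the error rate. The plan nowhere says that 0.05 applies at each look, and the cited guideline may be strict.
- That there is no stopping rule. There is one, by reference; what is missing is the threshold and the reference entry.

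Finally, treatment is chosen by the patient and can change weekly, and bias from that may exceed any multiplicity effect. This is true, and it limits how much a nominal error rate means, but it does not excuse leaving the primary outcome undefined.

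**Conclusion.** The outcome-status conflict is real on either reading of 3d and should be corrected. The 936 itself is not wrong: it is exact for one two-sided 0.05 test of hospitalization, and it supports nothing else. Power for intubation is about 6% on the plan's own yield and about 18% even if every participant were an inpatient. The 3213 does not apply to death, for which the plan's rates need about 35,000 per group.

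These results rest on the plan's event rates and on two-sided testing. The false-positive range also depends on the one-family premise and, at its upper end, on an assumed number of extra inpatients. The 80% power for hospitalization holds only if all 936 are out of hospital at entry, which the plan does not state.

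The interim point is minor: a missing threshold and reference, with no inflation shown.

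**What to change.** **Section 3f.** Name hospitalization as the single primary efficacy outcome. Make intubation and death secondary and descriptive, with 95% confidence intervals. Keep side effects as the safety outcome, outside the efficacy error rate.

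**Sections 2, 3d and 4.** Bring these into line with 3f, including the Aim 1 wording and the reference to Aims 3 and 4. State that 3213 per group applies to intubation (10% vs 8%) and not to death. State that the 312 + 624 counts only participants not in hospital at entry, or restate the power using the expected inpatient share.

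**Data Safety Monitoring Board paragraph (minor).** Add the guideline to the reference list. Write out the statistical threshold for an interim benefit claim on hospitalization; p<0.001 before the final test is one example, if it is consistent with the guideline. If the guideline sets another boundary, state that boundary with its error rate and sample size. Say whether Review 4 is an interim or the final analysis, and that the threshold does not restrict safety review.

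**Cost.** These are text edits, one reference and matching instructions to the board. The example threshold needs no more than 936 participants out of hospital at entry, but if inpatients were being counted in that figure, enrolment must rise or lower power be accepted. Intubation and death can no longer carry a primary claim, and an interim threshold this strict makes an early benefit claim harder. Confounding from patient-chosen and switching treatment is untouched and needs separate handling.
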